8.7. Unscheduled Visits

Unscheduled visits may occur at any time at the investigator's (or designee's) discretion and appropriate clinical and laboratory tests may be performed as clinically indicated.

If there is a potential clinically significant abnormality in hematology or chemistry assessments (particularly in platelet count) during the study, an unscheduled visit within the following week should occur to repeat laboratory assessments (further details are provided in Table 9 and Table 10). The investigator must inform and consult the sponsor (or designee) regarding any hematologic abnormality.

8.8. End of Treatment and/or Early Termination

When the participant permanently discontinues study drug, whether the participant is terminating the study early or the participant has completed the study, the appropriate EOT visit should be conducted (EOT1 or EOT2). If the EOT visit coincides with a regular study visit, the EOT evaluations corresponding with the study period will supersede those of that scheduled visit, and the data should be entered in the appropriate EOT visit in the eCRF. The participant should be encouraged to return for the follow-up visit (EOS).

8.9. Follow-Up

The safety follow-up period is the interval between the EOT visit and the scheduled follow-up visit (EOS), which should occur approximately 30 days after the EOT visit (or after the last dose of study drug if the EOT visit was not performed). Adverse events and SAEs must be reported up until 1) at least 30 days after the last dose of study drug or 2) until toxicities resolve, return to baseline, or are deemed irreversible, whichever is longer. Reasonable efforts should be made to have the participant return for the follow-up visit and report any AEs that may occur during this period. In exceptional cases when the participant cannot return to the site for the safety follow-up visit, the participant should be contacted by telephone/video call for assessment of AEs and SAEs and the site should properly document the contact.

9. ADVERSE EVENTS: DEFINITIONS AND PROCEDURES FOR RECORDING, EVALUATING, FOLLOW-UP, AND REPORTING

9.1. Definition of Adverse Event

Adverse Event Definition

- An AE is any untoward medical occurrence associated with the use of a drug in humans, whether or not it is considered drug-related.
- An AE can therefore be any unfavorable or unintended sign (including an abnormal laboratory finding), symptom, or disease (new or exacerbated) temporally associated with the use of study drug.

Additional Guidance for Events Meeting the Adverse Event Definition

- Any safety assessments (eg, ECG, vital signs measurements), including those that worsen from baseline, considered clinically significant in the medical and scientific judgment of the investigator (ie, not related to progression of underlying disease) are to be reported as an AE.
- Abnormal laboratory test results are to be reported as an AE if they are considered clinically meaningful, induce clinical signs or symptoms, require concomitant therapy, or require changes in study drug. Whenever possible, a diagnosis (eg, anemia, thrombocytopenia) should be recorded in the eCRF rather than the abnormal laboratory test result (eg, low Hgb, platelet count decreased).
- Exacerbation of a chronic or intermittent pre-existing condition/disease, including either an increase in the frequency and/or intensity of the condition, is to be reported as an AE.
- New conditions detected or diagnosed after the start of study drug administration are to be reported as an AE.
- Signs, symptoms, or the clinical sequelae of a suspected drug-drug interaction are to be reported as an AE.
- Signs and/or symptoms from dosing errors of a study drug (eg, overdose) or a concomitant medication are to be reported as an AE.
- "Lack of efficacy," "disease progression," or "failure of expected pharmacological action" will not be reported as an AE or SAE. Such instances will be captured in the efficacy assessments.

- A condition that leads to a medical or surgical procedure (eg, endoscopy, appendectomy) will be reported as an AE if it occurs after obtaining informed consent. The procedure should also be reported in the eCRF. If the condition was present before entering the study, then it should be captured as medical history.
- Pre-existing diseases or conditions with expected fluctuations in signs or symptoms should be reported as an AE only if the investigator judges the fluctuation to have worsened more than expected during study participation.

9.2. Definition of Serious Adverse Event

If an event is not an AE per the definition above, then it cannot be an SAE even if serious conditions are met (eg, hospitalization for signs/symptoms of the disease under study, death due to progression of disease).

A serious adverse event is defined as any untoward medical occurrence that, at any dose:

a. Results in death

b. Is life-threatening

The term "life-threatening" in the definition of "serious" refers to an adverse drug experience that places the participant, in the opinion of the initial reporter, at immediate risk of death from the adverse experience as it occurs. This does not include an adverse drug experience that, had it occurred in a more severe form, might have caused death.

c. Requires inpatient hospitalization or prolongation of existing hospitalization

In general, hospitalization signifies that the participant has been detained (involving at least an overnight stay) at the hospital or emergency ward for observation and/or treatment that would not have been appropriate in the physician's office or outpatient setting. Complications that occur during hospitalization are AEs. If a complication prolongs hospitalization or fulfills any other serious criteria, the event is serious. When in doubt as to whether hospitalization occurred or was necessary, the AE should be considered serious.

Hospitalization for elective treatment or planned surgery (eg, stent replacement, hip surgery) is not considered an SAE.

Hospitalization for medical interventions in which no unfavorable medical occurrence occurred (ie, elective procedures or routine medical visits) is not considered an SAE.

d. Results in persistent or significant disability/incapacity

• The term "disability" means a substantial disruption of a person's ability to conduct normal life functions. This definition is not intended to include experiences of relatively minor medical significance, such as uncomplicated headache, nausea, vomiting, diarrhea, influenza, and accidental trauma (eg, sprained ankle), that may interfere with or prevent everyday life functions but do not constitute a substantial disruption.

e. Is a congenital anomaly/birth defect

f. Is an important medical event

An important medical event is an event that may not result in death, be immediately life-threatening, or require hospitalization but may be considered serious when, based on appropriate medical judgment, the event may jeopardize the participant and may require medical or surgical intervention to prevent one of the outcomes listed in the above definition. Examples of such events include new invasive or malignant cancers; intensive treatment in an emergency department or at home for allergic bronchospasm, blood dyscrasias, or convulsions that do not result in hospitalization; or development of drug dependency or drug abuse. Secondary malignancies should always be considered SAEs.

9.3. Recording and Follow-Up of Adverse Events and/or Serious Adverse Events

Adverse Event and Serious Adverse Event Recording

- An AE/SAE that begins or worsens after informed consent is signed should be recorded on the Adverse Event Form in the eCRF. AEs/SAEs should be reported for randomized participants, but only SAEs need to be reported for screen failure participants. For randomized participants, conditions that were present at the time informed consent was given should be recorded on the Medical History Form in the eCRF. For detailed information, refer to the eCRF guidelines.
- When an AE/SAE occurs, it is the responsibility of the investigator to review all documentation (eg, hospital progress notes, laboratory reports, and diagnostic reports) related to the event.
- The investigator (or delegate) will then record all relevant AE/SAE information in the eCRF.
- It is **not** acceptable for the investigator to send photocopies of the participant's medical records in lieu of completing the Adverse Event Form in the eCRF.
- There may be rare instances when copies of medical records for certain cases are requested. In this case, all participant identifiers, with the exception of the participant number, will be redacted by the site staff on the copies of the medical records before submission. These records can be submitted to Incyte Pharmacovigilance by email/fax per the contact information listed in the Study Reference Manual or as per SAE completing guidelines.
- The investigator will attempt to establish a diagnosis of the event based on signs, symptoms, and/or other clinical information. Whenever possible, the diagnosis (not the individual signs/symptoms) will be documented as the AE/SAE. When a clear diagnosis cannot be identified, each sign or symptom should be reported as a separate AE/SAE.

To the extent possible, each AE/SAE should be evaluated to determine the following:

- The severity grade (CTCAE v5.0 Grade 1 to 5). See below for further instructions on the assessment of intensity.
- Whether there is at least a reasonable possibility that the AE is related to the study drug: suspected (yes) or not suspected (no). See below for further instructions on the assessment of causality.
- The start and end dates, unless unresolved at the final safety follow-up visit.
- The action taken with regard to study drug as a result of the AE/SAE(s).
- The event outcome (eg, not recovered/not resolved, recovered/resolved, recovering/resolving, recovered/resolved with sequelae, fatal, unknown).

- The seriousness, as per the SAE definition provided in Section 9.2.
- The action taken with regard to the event. Note: If an AE is treated with a concomitant medication or nondrug therapy, this action should be recorded on the Adverse Event Form and the treatment should be specified on the appropriate eCRF (eg, Prior/Concomitant Medications, Procedures, and Non-Drug Therapy).

Assessment of Intensity

The severity of AEs will be assessed using CTCAE v5.0 Grades 1 through 5. If an event is not classified by CTCAE, the severity of the AE will be graded according to the scale below to estimate the grade of severity.

The investigator will make an assessment of intensity for each AE and SAE reported during the study and assign it to 1 of the following categories:

- Grade 1: Mild; asymptomatic or mild symptoms; clinical or diagnostic observations only; treatment not indicated.
- Grade 2: Moderate; minimal, local, or noninvasive treatment indicated; limiting age-appropriate activities of daily living.
- Grade 3: Severe or medically significant but not immediately life-threatening; hospitalization or prolongation of hospitalization indicated; disabling; limiting self-care activities of daily living.
- Grade 4: Life-threatening consequences; urgent treatment indicated.
- Grade 5: Fatal.

Assessment of Causality

- The investigator is obligated to assess the relationship between study drug and each occurrence of each AE/SAE.
- A "reasonable possibility" of a relationship conveys that there are medical facts, evidence, and/or arguments to suggest a causal relationship, rather than that a relationship cannot be ruled out.
- The investigator will use clinical judgment to determine the possibility of a relationship.
- The investigator will also consult the RSI in the IB or Product Information for study drug, or marketed products, respectively, in making his/her assessment.
- Alternative causes, such as underlying or concurrent disease(s), concomitant therapy, and other risk factors, as well as the temporal relationship of the event to study drug administration, will be considered and investigated.
- For each AE/SAE, the investigator **must** document in the medical notes that he/she has reviewed the AE/SAE and has provided an assessment of causality.
- With regard to assessing causality of SAEs:

- There may be situations in which an SAE has occurred and the investigator has minimal information to include in the initial report. However, the causality assessment is one of the criteria used when determining regulatory reporting requirements. Therefore, it is very important that the investigator always make an assessment of causality based on the available information for every event before the initial transmission of the SAE.

- The investigator may change his/her opinion of causality in light of follow-up information and submit the updated causality assessment.

Follow-Up of Adverse Events and Serious Adverse Events

- The investigator is obligated to perform or arrange for the conduct of supplemental measurements and/or evaluations as medically indicated or as requested by the sponsor to elucidate the nature and/or causality of the AE or SAE as fully as possible. This may include additional laboratory tests or investigations, histopathological examinations, or consultation with other health care professionals.
- Once an AE is detected, it should be followed in the AE eCRFs until it has resolved or until it is judged to be permanent; assessment should be made at each visit (or more frequently if necessary) of any changes in severity, the suspected relationship to the study drug, the interventions required to treat the event, and the outcome.
- When the severity of an AE changes over time for a reporting period (eg, between visits), each change in severity will be reported as a separate AE.
- If a participant dies during participation in the study or during a recognized follow-up period, the investigator will provide the sponsor with a copy of any postmortem findings, including histopathology.
- Updated SAE information will be recorded in the originally completed eCRF and reported to Incyte Pharmacovigilance (via the AE and SAE eCRFs in the EDC) until resolution, stabilization, the event is otherwise explained, or the participant is lost to follow-up.
- Any updated SAE data (including SAEs being downgraded to nonserious) will be submitted to the sponsor (or designee) within 24 hours of receipt of the information.

See Appendix E for the management of PHL cases.

9.4. **Reporting of Serious Adverse Events**

Regardless of suspected causality (eg, relationship to study drug, study procedures), all SAEs occurring after the participant has signed the ICF through the last safety visit or at least 30 days after the last dose of study drug must be reported to the sponsor (or designee) immediately, without undue delay but not later than within **24 hours** of obtaining knowledge of its occurrence unless otherwise specified by the Protocol. The investigator will submit any updated SAE data to the sponsor (or designee) immediately, without undue delay but not later than within 24 hours of it being available.

Investigators are not obligated to actively seek SAE information after the safety follow-up visit or 30 days after the last dose of study drug. If the investigator learns of any SAE, including death, at any time during this period, and he/she considers the event to be reasonably related to the study drug or study participation, then the investigator must notify the sponsor (or designee) within 24 hours of becoming aware of the event.

After the initial AE/SAE report, the investigator is required to proactively follow each participant at subsequent visits/contacts. All SAEs will be followed until resolution, stabilization, the event is otherwise explained, or the participant is lost to follow-up (as defined in Section 7.3).

Prompt notification by the investigator to the sponsor regarding an SAE is essential so that legal obligations and ethical responsibilities toward the safety of participants and the safety of a study drug under clinical investigation are met.

If the SAE is not documented in the RSI of the IB for the study drug (new occurrence) and is thought to be related to the study drug, the sponsor or its designee may urgently require further

information from the investigator for expedited reporting to health authorities. The sponsor or its designee may need to issue an Investigator Notification to inform all investigators involved in any study with the same drug that this SAE has been reported. Suspected unexpected serious adverse reactions will be collected and reported to the competent authorities and relevant ethics committees in accordance with Directive 2001/20/EC or as per national regulatory requirements in participating countries.

The sponsor has a legal responsibility to notify both the local regulatory authority and other regulatory agencies about the safety of a study drug under clinical investigation. The sponsor will comply with country-specific regulatory requirements relating to safety reporting to the regulatory authority, IRB/IEC, and investigators.

Investigator safety reports must be prepared for suspected unexpected serious adverse reactions according to local regulatory requirements and sponsor policy and forwarded to investigators as necessary.

An investigator who receives an investigator safety report describing an SAE or other specific safety information (eg, summary or listing of SAEs) from the sponsor will review and then file it along with the IB and will notify the IRB/IEC, if appropriate, according to local requirements.

Serious Adverse Event Reporting

- Information about all SAEs is collected and recorded on the Adverse Event and Serious Adverse Event Forms in the eCRF.
- The investigator must report within 24 hours of learning of its occurrence any SAE via the EDC system (primary method) or by completing the Serious Adverse Event Report Form in English (only if the EDC system is not available). The contact information for Incyte Pharmacovigilance by email/fax is listed in the Study Reference Manual or as per the Incyte Reference Guide for Completing the Serious Adverse Event Report Form.
- In circumstances where the EDC system is not accessible for reporting SAE information (initial and/or follow-up SAE information) to the sponsor within 24 hours, refer to the Incyte Reference Guide for Completing the Serious Adverse Report Form. Once the EDC system is functional, the SAE report should be retrospectively added to the EDC system and follow-up should be completed through the EDC. The original copy of the Serious Adverse Event Report Form and the email or facsimile confirmation sheet must be kept at the study site (refer to the Incyte Reference Guide for Completing the Serious Adverse Event Report Form or Study Reference Manual for details and for the email address or fax number).
- Follow-up information is also recorded in the eCRF and transmitted to Incyte Pharmacovigilance via the EDC system. The follow-up report should include information that was not provided previously, such as the outcome of the event, treatment provided, action taken with study drug because of the SAE (eg, dose reduced, interrupted, or discontinued), or participant disposition (eg, continued or withdrew from study participation). Each recurrence, complication, or progression of the original event should be reported as follow-up to that event, regardless of when it occurs.

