2.3.3. Justification for Placebo

The comparison to placebo is relevant to better understand the effect of an oral systemic JAK1 inhibitor in the treatment of PN. The use of placebo is justified considering that there are no available PN-specific therapies to be used as a comparator and that delaying treatment does not pose excessive harm to patients (Millum and Grady 2013). In addition, participants who have a substantial worsening of PN during the placebo-controlled period may receive rescue therapy (see Section 6.6.4 for allowed recue therapies). After the 16-week placebo-controlled period, all participants will receive INCB054707

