9.2. Adverse Events

9.2.1. Adverse Event Definitions

A TEAE is any AE either reported for the first time or worsening of a pre-existing event after the first dose of study drug and up to 30 days after the last dose of study drug. Analysis of AEs will be limited to TEAEs, but data listings will include all AEs regardless of their timing in relation to study drug administration. For purposes of analysis, all AEs will be considered TEAEs unless the AE can unequivocally be defined as not treatment-emergent.

A TEAE in the PC period is any AE with a start time after the first dose of study drug in the PC period and until the end of the safety follow-up, or prior to the first dose in the extension period for participants who entered in to the extension period.

A TEAE in the extension period is any AE with a start time after the first dose of study drug in the extension period and until the end of the safety follow-up.

For participants who took only povorcitinib 45 or 75 mg during overall period, a TEAE is any AE with a start time after the first dose of study drug in the PC period and until the end of the safety follow-up.

Adverse events will be tabulated by MedDRA PT and SOC. Severity of AEs will be graded using the National Cancer Institute CTCAE v5.0. The CTCAE reporting guidelines and grading details are available on the Cancer Therapy Evaluation Program website.

The subset of AEs considered by the investigator to be related to study drug will be considered to be treatment-related AEs. If the investigator does not specify the relationship of the AE to study drug, the AE will be considered to be treatment-related. The incidence of AEs and treatment-related AEs will be tabulated. In addition, serious TEAEs will also be tabulated.

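### A serious adverse event that recurs at the same grade in a later study period can be missed in that period's serious-TEAE table, because Protocol 9.4 files recurrences as follow-up and SAP 9.2.1 assigns period by start time

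*Protocol*

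**What the plan says.** Protocol 9.4, under the heading on serious adverse event reporting, gives this rule: "Each recurrence, complication, or progression of the original event should be reported as follow-up to that event, regardless of when it occurs". It sets no time limit and makes no exception for an event that has resolved. The same bullet says "Follow-up information is also recorded in the eCRF and transmitted to Incyte Pharmacovigilance via the EDC system", so the rule reaches the study database as well as the safety database. Protocol 9.3 names the record to be updated: "Updated SAE information will be recorded in the originally completed eCRF and reported to Incyte Pharmacovigilance".

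Other passages point towards new records:

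- Protocol 9.3, on a severity that changes over time: "each change in severity will be reported as a separate AE".
- Protocol 9.3, on recording: "An AE/SAE that begins or worsens after informed consent is signed should be recorded on the Adverse Event Form in the eCRF".
- Protocol 9.2 treats a complication that arises in hospital as an AE.

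Among the items to be determined for each AE or SAE, 9.3 lists "The start and end dates, unless unresolved at the final safety follow-up visit". Neither document says what start date a recurrence takes.

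SAP 9.2.1 opens with a general TEAE definition that includes worsening of an existing event, and it treats doubtful cases as treatment-emergent. The definitions for each period then use start time alone. For the extension: "A TEAE in the extension period is any AE with a start time after the first dose of study drug in the extension period". The placebo-controlled and overall-period definitions have the same form, counted from the first placebo-controlled dose. SAP 9.2.2 counts participants with serious TEAEs, not episodes. Protocol 2.3.3 states: "After the 16-week placebo-controlled period, all participants will receive INCB054707".

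**The concern.** The recording rule and the counting rule do not fit together. The SAP finds the period of an AE from its start time. Protocol 9.4 tells the site to attach a recurrence to the earlier SAE, and 9.3 sends the update to the earlier record. A second episode recorded only in this way brings no start time of its own into the analysis data.

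Take a participant on placebo who has a serious infection that resolves, and who has it again at the same grade on povorcitinib in the extension. The first episode is correctly counted under placebo. The second can be absent from the extension table, although it occurred on active drug. Everyone in the extension is on active drug, so an omission there can only lower a serious-TEAE count on povorcitinib.

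The conflict between 9.3 and 9.4 adds a second problem. A site that sees an SAE progress to a higher grade is told by one section to open a separate AE and by the other to file follow-up. Different sites may reasonably do different things.

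**Working it through.** The plan gives no figure on this point, so there is none to reproduce. The check sets the recording rules of Protocol 9.2 to 9.4 against the counting rules of SAP 9.2.1 and 9.2.2, one case at a time.

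1. **SAE begins in the placebo-controlled period, resolves, and recurs at the same grade in the extension.** The severity rule in 9.3 is not triggered because the grade is unchanged. Under 9.4 the recurrence is follow-up. If it is recorded only on the earlier record, no start time falls after the first extension dose and the participant can be missed in the extension table.
2. **SAE begins in screening, resolves, and recurs at the same grade after Day 1.** On the same reading the start time precedes the first dose, so the period definition is not met and the event can be missed. The general TEAE definition and the default to treatment-emergent could bring it in. The SAP does not say whether they override the period definition.
3. **Recurrence or progression at a different grade.** Protocol 9.3 makes it a separate AE, which can carry its own start date and fall in the right period. Protocol 9.4 makes it follow-up. The result depends on which section the site follows.
4. **Recurrence within the same period and dose.** The participant is already counted, so participant-level incidence does not change.
5. **Overall tables for participants who took only 45 mg or only 75 mg.** There is one dose and one window from the first placebo-controlled dose. An event that began after that dose stays under the right dose even if a recurrence is folded into it.

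The exposed cases are therefore 1 and 2. Case 3 is open until the sections are reconciled.

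**Size of one missed participant.** In a group of n it is 100 × 1/n percentage points.

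- Planned randomized group (Protocol Table 2 and 10.1): n = 35, so 100 × 1/35 = 2.9 points.
- Extension subgroups are split by Week 16 response and treatment path (SAP 5.2), and their sizes are not given. As an illustration only, take the 15% placebo response assumed for sample size, apply it to itch alone, and let all 35 placebo participants enter the extension. Responders: 35 × 0.15 = 5.25, and 100 × 1/5.25 = 19.0 points. Nonresponders: 35 × 0.85 = 29.75, and 100 × 1/29.75 = 3.4 points.

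The 19.0 shows how small such a cell could be. Any single event in it would have that effect. Actual cells will differ, because the extension grouping uses IGA as well as itch and some participants will leave before Week 16.

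**The case against.** The strongest reply is that 9.4 concerns reporting to the sponsor and does not define analysis counts. SAEs go on both an Adverse Event Form and a Serious Adverse Event Form, so linking a recurrence to the earlier case does not in itself forbid a new dated AE record. The instruction in 9.3 to record what begins or worsens could support one. The eCRF guidelines and the SAE completion guide, to which the protocol refers, may settle the matter and are not available here. This stands as far as it goes: a retained first onset date is an inference from silence. It does not remove the problem, because the only explicit instruction on SAE recurrence points to the old record and follow-up is stored in the eCRF.

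A reader might infer more than the documents support:

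- *That a recurrent SAE is never counted where it recurs.* Cases 3 to 5 contradict this.
- *That a screening-onset SAE recurring on treatment is definitely not treatment-emergent.* The general definition and the default in SAP 9.2.1 leave this unsettled.
- *That the error always favours povorcitinib.* In the extension an omission can only lower a count on active drug. A screening-onset recurrence, however, could be missed in any arm of the placebo-controlled period, placebo included.
- *That a sizeable share of all SAE episodes would be lost.* This needs an assumed number of SAEs and an episode denominator, and the SAP tables count participants.
- *That recurrence after restarting drug is hidden.* The planned tables do not assess rechallenge. A linked case that records the action taken with study drug keeps the recurrence visible to case review.

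**Conclusion.** The point holds in limited form. Following the stated rules can leave a same-grade SAE that recurs across a period boundary out of the serious-TEAE table for the period and treatment in which it recurred. It rests on one assumption: that sites do what 9.4 and 9.3 say and update the earlier record without opening a new dated one.

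The number affected is likely to be small. Protocol 2.4 reports no serious TEAEs in the two earlier hidradenitis suppurativa studies, although those lasted only up to 8 weeks. One missed participant is about 2.9 percentage points in a group of 35, and more in a smaller extension subgroup. The effect is on descriptive safety tables; no efficacy test is touched. It is still worth correcting, because it follows from rules that the plan states and is cheap to repair.

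**What to change.** Three changes are needed.

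1. In Protocol 9.4, state that a recurrence after resolution gets its own AE/SAE record with its own onset date, cross-referenced to the original SAE case. Carry this into the eCRF and SAE completion guidelines.
2. Reconcile what 9.4 says on progression and complications with 9.3, where a severity change is a separate AE, and with 9.2, where a complication in hospital is an AE. Neither should be left as follow-up only.
3. In SAP 9.2.1, add the worsening clause of the general TEAE definition to each period-specific definition. An event already present that worsens after the first dose of a period is then counted in that period.

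The start-time rule can then place each new episode in the right period and treatment. The cost is a few sentences in the protocol, guidelines and SAP, and a few more linked SAE records to reconcile in the safety database.
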